7.1.3.2 Treatment Period

Study Day 1/Visit 1

For Cohort 1, patients will undergo a Screening/Inclusion Visit that coincides with Visit 9 of Study A4250-005.

For Cohort 1: Obtain written informed consent

For Cohort 2: Albireo PRO/ObsRO eDiary review for compliance and eligibility criteria (see Inclusion Criteria 4 [Cohort 2, excluding BRIC], [Section 7.2.1](#)).

The following procedures will be conducted for both cohorts:

- Assess inclusion/exclusion criteria ([Section 7.2](#))
- Document concomitant medications
- Physical examination ([Section 10.2.5](#)) and vital signs ([Section 10.2.6](#))
- Skin examination ([Section 10.2.5](#))
- Albireo PRO/ObsRO eDiary training, compliance requirements, and instructions to continue recording of pruritus ([Appendix 2](#))
- Clinical chemistry, hematology, and urinalysis ([Section 10.2.1](#))
- Serum bile acids ([Section 9.2.1](#))
- p-C4 and autotaxin
- Alfa-fetoprotein (AFP)
- Vitamins A, E, and 25-hydroxy vitamin D ([Section 10.2.1](#))
- Abdominal ultrasound ([Section 10.2.7](#))
- Fibroscan, where available ([Section 9.2.8](#))
- Administer QoL (Pediatric Quality of Life Inventory [PedsQL]) questionnaire
- Serum pregnancy test for girls who have reached menarche (only for patients in Cohort 1). Please see [Appendix 6](#) for contraceptive requirements
- Patient/caregiver/clinician complete the patient global impression of symptoms (PGIS) and the patient global impression of change (PGIC)
- AE monitoring
- Study drug is dispensed

Week 4/Visit 2

The following procedures and assessments will be conducted:

- Document concomitant medications
- Vital signs ([Section 10.2.6](#))
- Skin examination ([Section 10.2.5](#))
- Albireo PRO/ObsRO eDiary review for compliance

- Clinical chemistry and hematology ([Section 10.2.1](#))
- INR
- Serum bile acids ([Section 9.2.1](#))
- p-C4 and autotaxin
- Patient/caregiver/clinician complete the PGIS and the PGIC
- Urine pregnancy test for girls who have reached menarche
- AE monitoring
- Evaluation of study drug compliance
- Study drug is dispensed

Week 8/Telephone contact 1

- A study nurse will contact patients via telephone for AE monitoring 4 weeks after Visit 2, at Week 8

Week 12/Visit 3

As of Protocol Amendment 6, patients entering Cohort 2 will start treatment at 40 µg/kg/day with the possibility to dose escalate to 120 µg/kg/day after 12 weeks (Visit 3) if there is no improvement in pruritus based on investigator judgment.

The following procedures and assessments will be conducted (all patients):

- Document concomitant medications
- Physical examination ([Section 10.2.5](#)) and vital signs ([Section 10.2.6](#))
- Skin examination ([Section 10.2.5](#))
- Albireo PRO/ObsRO eDiary review for compliance
- Clinical chemistry and hematology ([Section 10.2.1](#))
- INR
- Serum bile acids ([Section 9.2.1](#))
- Vitamins A, E, and 25-hydroxy vitamin D ([Section 10.2.1](#))
- Patient/caregiver/clinician complete the PGIS and the PGIC
- Urine pregnancy test for girls who have reached menarche
- AE monitoring
- Evaluation of study drug compliance; dosage form acceptability questions will be asked of the caregiver and/or patient

- Study drug is dispensed

Week 18/Telephone contact 2

- A study nurse will contact patients via telephone for AE monitoring 6 weeks after Visit 3, at Week 18

Weeks 22 and 46/Visits 4 and 7

The following procedures and assessments will be conducted:

- Document concomitant medications
- Vital signs ([Section 10.2.6](#))
- Albireo PRO/ObsRO eDiary review for compliance
- INR
- Serum bile acids ([Section 9.2.1](#))
- Vitamins A, E, and 25-hydroxy vitamin D ([Section 10.2.1](#))
- Urine pregnancy test for girls who have reached menarche
- AE monitoring

Weeks 24 and 48/Visits 5 and 8

The following procedures and assessments will be conducted:

- Document concomitant medications
- Skin examination ([Section 10.2.5](#))
- Physical examination at Visit 5 ([Section 10.2.5](#)) and vital signs ([Section 10.2.6](#))
- Albireo PRO/ObsRO eDiary review for compliance
- Clinical chemistry, hematology, and urinalysis ([Section 10.2.1](#))
- Serum bile acids ([Section 9.2.1](#))
- p-C4 and autotaxin
- AFP
- Abdominal ultrasound ([Section 10.2.7](#))
- Fibroscan, where available ([Section 9.2.8](#))
- Administer PedsQL questionnaire
- Patient/caregiver/clinician complete the PGIS and the PGIC
- Urine pregnancy test for girls who have reached menarche
- AE monitoring

- Evaluation of study drug compliance
- Study drug is dispensed

Weeks 30 and 54/Telephone contacts 3 and 5

- A study nurse will contact patients via telephone for AE monitoring 6 weeks after Visits 5 and 8, at Weeks 30 and 54, respectively

Weeks 36 and 60/Visits 6 and 9

The following procedures and assessments will be conducted:

- Document concomitant medications
- Vital signs ([Section 10.2.6](#))
- Albireo PRO/ObsRO eDiary review for compliance
- Clinical chemistry and hematology ([Section 10.2.1](#))
- INR
- Vitamins A, E, and 25-hydroxy vitamin D ([Section 10.2.1](#))
- Serum bile acids ([Section 9.2.1](#))
- Urine pregnancy test for girls who have reached menarche
- AE monitoring
- Evaluation of study drug compliance; dosage form acceptability questions will be asked of the caregiver and/or patient (only at Visit 6)
- Study drug is dispensed

Weeks 42 and 66/Telephone contacts 4 and 6

- A study nurse will contact patients via telephone for AE monitoring 6 weeks after Visits 6 and 9, at Weeks 42 and 66, respectively

Week 70/Visit 10

The following procedures and assessments will be conducted:

- Document concomitant medications
- Vital signs ([Section 10.2.6](#))
- Albireo PRO/ObsRO eDiary review for compliance
- Serum bile acids ([Section 9.2.1](#))
- INR
- Vitamins A, E, and 25-hydroxy vitamin D ([Section 10.2.1](#))

- Urine pregnancy test for girls who have reached menarche
- AE monitoring

7.1.3.3 End of Treatment/Early Termination/Start of Optional Extension Period

Week 72/Visit 11

The last dose of study drug will be administered in the morning the day before the visit and the following assessments will be performed:

- Document concomitant medications
- Physical examination ([Section 10.2.5](#)) and vital signs ([Section 10.2.6](#))
- Skin examination ([Section 10.2.5](#))
- Albireo PRO/ObsRO eDiary review for compliance
- Clinical chemistry, hematology, and urinalysis ([Section 10.2.1](#))
- Serum bile acids ([Section 9.2.1](#))
- p-C4 and autotaxin
- AFP
- Abdominal ultrasound ([Section 10.2.7](#))
- Fibroscan, where available ([Section 9.2.8](#))
- Administer PedsQL questionnaire
- Urine pregnancy test for girls who have reached menarche
- Patient/caregiver/clinician complete the PGIC and PGIS
- AE monitoring
- Evaluation of study drug compliance; dosage form acceptability questions will be asked of the caregiver and/or patient
- Liver biopsy (if required; see [Section 9.2.10](#))
- Patient/Caregiver decide whether to continue A4250 treatment
- Dispensing of drug for optional Extension Period (if applicable)

7.1.3.4 Follow-up Visit

Week 76/Visit 12 (Patients/Caregivers not participating in Optional Extension Period)

Patients will return to the study site 28 days after Visit 11 or the last dose of study drug (for those patients who prematurely withdraw) for the following assessments:

- Document concomitant medications

- Vital signs ([Section 10.2.6](#))
- Albireo PRO/ObsRO eDiary review for compliance
- Clinical chemistry and hematology ([Section 10.2.1](#))
- INR
- Serum bile acids ([Section 9.2.1](#))
- Urine pregnancy test for girls who have reached menarche
- AE monitoring

7.1.3.5 Optional Extension Period

Week 88 and every 16 weeks thereafter up to commercial availability of drug

- Document concomitant medications
- Vital signs ([Section 10.2.6](#))
- Clinical Chemistry ([Section 10.2.1](#))
- Serum bile acids ([Section 9.2.1](#))
- Vitamins A, E, and 25-hydroxy vitamin D ([Section 10.2.1](#))
- INR
- Urine pregnancy test for girls who have reached menarche
- Administer PedsQL questionnaire
- Patient/caregiver/clinician complete the PGIS and the PGIC
- Evaluation of study drug compliance
- Study drug is dispensed
- AE monitoring

7.1.3.6 Optional Extension Period End of Treatment

Upon commercial availability, patients should complete the End of Treatment (EOT) visit before starting commercial drug. For patients who decide to withdraw from the optional extension period prior to commercial availability, patients should immediately return to the site for the following EOT assessments:

- Document concomitant medications
- Vital signs ([Section 10.2.6](#))
- Clinical Chemistry ([Section 10.2.1](#))
- Serum bile acids ([Section 9.2.1](#))

- Vitamins A, E, and 25-hydroxy vitamin D ([Section 10.2.1](#))
- INR
- Urine pregnancy test for girls who have reached menarche
- Administer PedsQL questionnaire
- Patient/caregiver/clinician complete the PGIS and the PGIC
- Evaluation of study drug compliance
- AE monitoring

7.2 Study Population

Cohort 1 will consist of approximately 60 children who completed 24 weeks, or who withdrew after a minimum of 12 weeks of treatment due to intolerable symptoms in Study A4250-005 and meeting all inclusion criteria and no exclusion criteria are eligible for this study. Patients who withdraw from A4250-005 due to a study drug related AE will not be eligible.

Cohort 2 will consist of approximately 60 patients with any type of PFIC who have elevated serum bile acids and cholestatic pruritus and who either (1) do not meet eligibility criteria for Study A4250-005 (PEDFIC 1) or (2) do meet the eligibility criteria for A4250-005 after recruitment of study A4250-005 has been completed. Up to 40 patients post biliary diversion surgery are allowed to participate in Cohort 2.

7.2.1 Inclusion Criteria

Cohort 1:

1. Completion of the 24-week Treatment Period of Study A4250-005 or withdrawn from Study A4250-005 due to patient/caregiver judgment of intolerable symptoms after completing at least 12 weeks of treatment. Patients who withdraw from A4250-005 due to a study drug related AE will not be eligible.
2. Signed informed consent and assent as appropriate. Patients who turn 18 years of age (or legal age per country) during the study will be required to re-consent to remain on the study.
3. Patients expected to have a consistent caregiver for the duration of the study.
4. Caregivers (and age-appropriate patients) must be willing and able to use an eDiary device as required by the study.

Cohort 2:

1. A male or female patient of any age, with a clinical diagnosis of PFIC, including episodic forms (i.e., BRIC), and with a body weight ≥ 5 kg at Visit S-1.
2. Patient must have clinical genetic confirmation of PFIC.

3. Patients with PFIC, excluding BRIC, must have elevated serum bile acid concentration, specifically measured to be $\geq 100 \mu\text{mol/L}$, taken as the average of 2 samples at least 7 days apart (Visits S-1 and S-2) prior to the Screening/Inclusion Visit (Visit 1).
4. Patients with PFIC, excluding BRIC, must have history of significant pruritus and a caregiver-reported observed scratching or patient-reported itching (for patients >18 with no caregiver-reported observed scratching) in the eDiary average of ≥ 2 (on 0 to 4 scale) in the 2 weeks prior to the Screening/Inclusion Visit (Visit 1).
5. Patients with episodic forms of PFIC (i.e., BRIC) must have an emerging flare characterized by clinically significant pruritus and elevated serum bile acid levels/cholestasis as judged by the investigator.
6. Patient and/or legal guardian must sign informed consent (and assent) as appropriate. Patients who turn 18 years of age (or legal age per country) during the study will be required to re-consent in order to remain in the study.
7. Age appropriate patients are expected to have a consistent caregiver for the duration of the study.
8. Caregivers and age-appropriate patients (≥ 8 years of age, if able) must be willing and able to use an eDiary device as required by the study.

7.2.2 Exclusion Criteria

Patients meeting any of the following criteria at Visit 1 or Visit S-1 will not be eligible for study participation:

Cohort 1:

1. Decompensated liver disease: coagulopathy, history, or presence of clinically significant ascites, variceal hemorrhage, and/or encephalopathy.
2. Sexually active males and females who are not using a reliable contraceptive method with $\leq 1\%$ failure rate (such as hormonal contraception, intra-uterine device, or complete abstinence) throughout the duration of the study and 90 days thereafter (from signed informed consent through 90 days after last dose of study drug). See [Appendix 6](#) for further details.
3. Patients not compliant with treatment in study A4250-005.
4. Any other conditions or abnormalities which, in the opinion of the investigator or Medical Monitor, may compromise the safety of the patient, or interfere with the patient participating in or completing the study.

Cohort 2:

1. Known pathologic variations of the ABCB11 gene that have been demonstrated to result in complete absence of the BSEP protein.

2. Patient with past medical history or ongoing presence of other types of liver disease including, but not limited to, the following:
 - a) Biliary atresia of any kind.
 - b) Suspected or proven liver cancer or metastasis to the liver on imaging studies.
 - c) Histopathology on liver biopsy is suggestive of alternate non-PFIC related etiology of cholestasis.
- Note: Patients with clinically significant portal hypertension are allowed.
3. Patient with a past medical history or ongoing presence of any other disease or condition known to interfere with the absorption, distribution, metabolism (specifically bile acid metabolism), or excretion of drugs in the intestine, including but not limited to, inflammatory bowel disease.
4. Patient with past medical history or ongoing chronic (i.e., >3 months) diarrhea requiring intravenous fluid or nutritional intervention for treatment of the diarrhea and/or its sequelae.
5. Patient has a confirmed past diagnosis of infection with human immunodeficiency virus or other present and active, clinically significant, acute, or chronic infection, or past medical history of any major episode of infection requiring hospitalization or treatment with parenteral anti-infective treatment within 4 weeks of treatment start (Study Day 1) or completion of oral anti-infective treatment within 2 weeks prior to start of Screening Period.
6. Any patient with suspected or confirmed cancers except for basal cell carcinoma, and non-liver cancers treated at least 5 years prior to Screening with no evidence of recurrence.
7. Patient has had a liver transplant, or a liver transplant is planned within 6 months of the Screening/Inclusion Visit.
8. Decompensated liver disease, coagulopathy, history, or presence of clinically significant ascites, variceal hemorrhage, and/or encephalopathy.
9. INR >1.4 (the patient may be treated with Vitamin K intravenously, and if INR is \leq 1.4 at resampling the patient may be included).
10. Serum ALT $>10 \times$ upper limit of normal (ULN) at Screening.
11. Serum ALT $>15 \times$ ULN at any time point during the last 6 months unless an alternate etiology was confirmed for the elevation.
12. Total bilirubin $>10 \times$ ULN at Screening.
13. Patient suffers from uncontrolled, recalcitrant pruritic condition other than PFIC. Examples include, but not limited to, refractory atopic dermatitis or other primary pruritic skin diseases.

14. Any patient who is pregnant or lactating or who is planning to become pregnant within 72 weeks of the Screening/Inclusion Visit.
15. Sexually active males and females who are not using a reliable contraceptive method with $\leq 1\%$ failure rate (such as hormonal contraception, intrauterine device, or complete abstinence) throughout the duration of the study and 90 days thereafter (from signed informed consent through 90 days after last dose of study drug). See [Appendix 6](#) for further details.
16. Patient with a past medical history of alcohol or substance abuse will be excluded. Patient must agree to refrain from illicit drug and alcohol use during the study.
17. Administration of bile acid or lipid binding resins and medications that slow GI motility (Refer to [Appendix 1](#) – Concomitant Medications Guidelines).
18. Patient has had investigational exposure to a drug, biologic agent, or medical device within 30 days prior to Screening, or 5 half-lives of the study agent, whichever is longer.
19. Any other conditions or abnormalities which, in the opinion of the investigator or Medical Monitor, may compromise the safety of the patient, or interfere with the patient participating in or completing the study.

7.2.3 Withdrawal of Patients

Patients/caregivers will be informed that they have the right to withdraw from the study at any time, without prejudice to their medical care, and that they are not obliged to state their reasons.

Any withdrawal, and reasons for withdrawal, must be fully documented in the eCRF and source documents and the patient followed by the investigator/investigative staff. Withdrawn patients will not be replaced.

Patients will be withdrawn in the following circumstances:

- A patient's/caregiver's desire for withdrawal for any reason
- Lost to follow-up (every effort must be made to contact the patient/caregiver; a certified letter must be sent)
- An AE which, in the opinion of the investigator, necessitates withdrawal
- Death
- A patient's/caregiver's substantial non-compliance (eDiary and study drug compliance) or protocol violation
- An investigator's opinion that continuing the patient in the study is not appropriate. The investigator may withdraw a patient at any time, if it is considered to be in the patient's best interest
- Liver transplantation

The reason and the date the patient is withdrawn from the study will be documented in the eCRF and source documents. If a patient is withdrawn from further treatment with the study drug, the investigator/investigative staff will attempt to complete all Visit 11 procedures at the time the patient is prematurely withdrawn from the study. The investigator/investigative staff will also attempt to complete all Visit 12 procedures 28 days following premature withdrawal (i.e., 28 days following the final dose of the study drug).

If a patient discontinues prior to Week 72, additional telephone contacts will be made every 3 months after the Follow-up Visit (Visit 12) up to Week 72 to gather whether or not the patient has had biliary diversion or liver transplantation, and of ongoing TEAEs at the time of discontinuation have resolved. The telephone calls will take place up until 72 weeks even if the patient has biliary diversion or liver transplant.

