Patients/caregivers will be instructed to fill in the electronic diary (eDiary) every morning and evening for the first 24 weeks (Visit 1 through Visit 5) and the 21 days before each clinic visit thereafter (Visit 6 through Visit 12). In addition, Cohort 2 patients/caregivers will be instructed to fill in the eDiary during the screening period. Patients participating in the optional extension period will stop eDiary entries at Visit 11. The eDiary will include patient reported outcome (PRO) and observer-reported outcome (ObsRO) items for evaluation of itching (PRO), scratching (ObsRO), and sleep disturbance (PRO and ObsRO). Observer-reported outcomes in patients of all ages will be recorded by a caregiver. If possible, the same caregiver will complete the ObsRO items throughout the study. Additionally, caregivers will be requested to report in the diary the time that study drug was administered during the Treatment Period.

The patient will return to the clinic after 4 weeks and 12 weeks and thereafter every 10 to 12 weeks for follow-up measurements. Between the clinic visits there will be a telephone contact with the patient/caregiver to report AEs.

At Visit 11, patients will be offered the choice to continue receiving A4250 treatment in an optional extension period. In the extension period the patient will continue to receive A4250 at the same dose as at the end of the 72-week treatment period, returning to clinic every 16 weeks until the drug is commercially available, provided continued use is supported by the risk-benefit profile and the subject has not been previously withdrawn or discontinued from study.

If the patient is prematurely withdrawn from the study, all assessments scheduled for Visit 11 will be performed at the time the patient withdraws. If a patient participating in the optional extension study withdraws prior to commercial drug availability, all assessments scheduled for the optional Extension Period End of Treatment visit will be performed.

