If a liver biopsy is performed according to the local regulations or standard of care at any time during A4250-008, the biopsy results should be recorded in the electronic case report form (eCRF). If the patient had liver biopsy results collected in study A4250-005 or prior to Week 24 in study A4250-008, the patient will be asked to consent to a follow-up liver biopsy, if allowed per local regulations, at Visit 11, unless 2 prior liver biopsy results have been collected with at least 1 year between biopsies. Liver biopsies will not be performed in Spain.

For those not participating in the optional extension period, Visit 12 will take place 28 days after Visit 11. All patients prematurely withdrawn will have this visit 28 days after the last dose of study drug for AE and other follow-up.

If a patient discontinues prior to Week 72, additional telephone contacts will be made every 3 months after the Follow-up Visit (Visit 12) up to Week 72 to gather whether or not the patient

has had biliary diversion or liver transplantation, and if TEAEs ongoing at the time of discontinuation have resolved. The telephone calls will take place up until 72 weeks even if the patient has biliary diversion or liver transplant.

Details of study assessments are provided in the schedule of assessments ([Table 1](#) and [Table 2](#)).

Figure 1 Study Design

QD: once daily; T: telephone contact; V: study visit; VS: Visit Screening

Note: Visit 1 coincides with Visit 9 of Study A4250-005. Patients who are not tolerating the 120 µg/kg/day dose may be down-titrated to the 40 µg/kg/day dose following a minimum of 1 week of treatment. The patient can return to the higher dose as soon as deemed appropriate.

This figure is only applicable to Cohort 2 up to Protocol Amendment 5. [Figure 2](#) presents the study design for Cohort 2 as of Protocol Amendment 6.

Figure 2 Study Design for Cohort 2 as of Protocol Amendment 6

QD: once daily; T: telephone contact; V: study visit; VS: Visit Screening

Note: As of Protocol Amendment 6, patients entering Cohort 2 will start treatment at 40 µg/kg/day with the possibility to dose escalate to 120 µg/kg/day after 12 weeks if there is no improvement in pruritus based on investigator judgment. The patient can return to the lower dose if the 120 µg/kg/day dose is not tolerated following a minimum of 1 week of treatment.

End of Study

The end of the study is defined as follows:

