		Screening/ Initial Visit	4 weeks	12 weeks	22 weeks	24 weeks	36 weeks	46 weeks	48 weeks	60 weeks	70 weeks	72 weeks		
Study Activity		76 weeks												
Study Days (±window)	-56- (-35) ±2	-28- (-7) ±2	1	28 (±5)	84 (±7)	154 (±7)	168 (±7)	252 (±7)	322 (±7)	336 (±7)	420 (±7)	490 (±7)	504 (±7)	532 (±7)
Clinic Visits	Visit S-1	Visit S-2	Visit 1a	Visit 2	Visit 3	Visit 4	Visit 5	Visit 6	Visit 7	Visit 8	Visit 9	Visit 10	11/EOT /Start of Optmnl Extension Period ¹¹	Visit 12 ^c
Fibroscan (where available)			X				X			X			X	
QoL questionnaire (PedsQL)			X				X			X			X	
Patient/Caregiver/Clinician Patient Global Impression of Change			X ¹¹	X	X		X			X			X	
Patient/Caregiver/Clinician Patient Global Impression of Symptoms				X	X	X	X	X	X	X	X	X	X	
Pregnancy test ¹¹	x ¹¹	X	x ¹¹	X	X	X	X	X	X	X	X	X	X	X
Telephone contact			Patients will be contacted via telephone for adverse event monitoring at Weeks 8, 18, 30, 42, 54, and 66											
Liver biopsy ¹¹													X	
Study drug dispensed ¹¹			X	X	X		X	X		X	X		X ¹¹	

Study Activity	Screening Period (Cohort 2 only)		Treatment Period										Follow-up Period ^h	
			Screening/ Inclusion Visit	4 weeks	12 weeks	22 weeks	24 weeks	36 weeks	46 weeks	48 weeks	60 weeks	70 weeks		
Study Days (\pm window)	-56- (-35) ± 2	-28- (-7) ± 2	1	28 (± 5)	84 (± 7)	154 (± 7)	168 (± 7)	252 (± 7)	322 (± 7)	336 (± 7)	420 (± 7)	490 (± 7)	504 (± 7)	532 (± 7)
Clinic Visits	Visit S-1	Visit S-2	Visit 1a	Visit 2	Visit 3	Visit 4	Visit 5	Visit 6	Visit 7	Visit 8	Visit 9	Visit 10	Visit 11/EOT /Start of Optional Extension Period ⁱ	Visit 12 ^c
Adverse events ^o p	Continuous collection													
Study drug compliance evaluated				X	xq		X	xq		X	X		xq	

eCRF: electronic case report form; eDiary: electronic diary; EOT: end of treatment; p-C4: plasma 7a Hydroxy 4-cholesten-3-one; PedsQL: pediatric quality of life; QoL: quality of life.

a For patients in Cohort I, Visit 1 coincides with Visit 9 in Study A4250-005. Assessments that have been performed at Visit 9 during Study A4250-005 will not be repeated.

b Assessments must also be performed at the time a patient is prematurely withdrawn from the study. If a patient discontinues prior to week 72, additional phone contact will be made every 3 months up to a total study participation of 72 weeks to assess if the patient has had biliary diversion or liver transplantation.

c Assessments must be performed 28 days following the final dose of study drug.

d Only for Cohort 1.

e Includes current medications.

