11.2.2.2 Missing Data

Missing data will be reported descriptively. In general, imputations of missing observations will not be made. Any additional sensitivity analysis concerning missingness and details regarding handling of missing data will be described in the statistical analysis plan (SAP).

Continued collection of efficacy data for patients who discontinue treatment will be made as far as possible.

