11.2.2.4 Subject Disposition

The following will be summarized overall by Cohort:

- Patients enrolled (who signed the informed consent)
- Patients treated
- Patients completing treatment
- Patients discontinuing treatment and reason
- Patients completing the study
- Patients withdrawing early (including withdrawal reason)

Additionally, patients enrolled, included in the FAS will be summarized by region by Cohort.

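### Section 7.2.3 makes non-compliance or protocol violation a mandatory ground for study withdrawal, which gives up obtainable on-treatment Week 70/72 values, and leaves efficacy collection after drug stop only partly carried out

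*Protocol*

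**What the plan says.** **Withdrawal grounds.** Protocol 7.2.3 states that patients will be withdrawn in a list of circumstances. One of them is "substantial non-compliance (eDiary and study drug compliance) or protocol violation". A separate bullet covers the investigator's opinion and the patient's best interest.

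**Stopping drug.** The same section continues: "If a patient is withdrawn from further treatment with the study drug", Visit 11 procedures are attempted when the patient is prematurely withdrawn from the study. Visit 12 follows 28 days after premature withdrawal, which the text equates with 28 days after the final dose. Section 7.1.1 agrees: "If the patient is prematurely withdrawn from the study, all assessments scheduled for Visit 11 will be performed at the time the patient withdraws".

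**Afterwards.** Section 7.1.1 says "additional telephone contacts will be made every 3 months after the Follow-up Visit (Visit 12) up to Week 72", to ask about biliary diversion, liver transplantation and resolution of ongoing TEAEs. Table 1, footnote b, says "additional phone contact will be made every 3 months up to a total study participation of 72 weeks". The optional extension is closed to patients previously withdrawn or discontinued.

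**Analysis side.** Section 11.2.2.2 says "Continued collection of efficacy data for patients who discontinue treatment will be made as far as possible", and that missing observations are in general not imputed. Section 11.2.2.4 tabulates treatment discontinuation and early withdrawal as separate items. Section 11.2.2.5 defines the bile acid end value as the mean of Weeks 70 and 72.

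**The concern.** The non-compliance bullet is mandatory in form, and it ends study participation rather than only dosing. Poor diary completion does not prevent a blood draw or a height measurement. A patient with a thin diary who still takes drug could give the Week 70/72 bile acid value (primary for EU and rest of world, secondary for US) and the Week 72 growth, APRI/Fib-4 and PELD/MELD values. The rule removes that patient, and with imputation generally excluded the value is lost. Cohort 1's objective is a sustained effect, so late values matter.

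The second part concerns patients who stop drug. Because stopping drug is run together with leaving the study, the commitment in 11.2.2.2 has no clinic visit behind it once Visit 12 is past. Patients who are withdrawn or stop drug may differ from those who stay, so the loss could be selective. A SAP can choose how to handle missing values, but it cannot supply visits that were not held.

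**Working it through.** The plan gives no figure on this point. Its one power figure (11.1, approximately 89% to 96% for n = 48 to 60) concerns diversion, transplantation or death. An exact binomial check with a Clopper-Pearson upper bound below 30% and a true rate of 10% gives 89.8% at n = 48 (at most 7 events) and 96.6% at n = 60 (at most 10 events). That reproduces it. Calls continue to ask about diversion and transplantation, so nothing here shows that figure to be wrong.

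**1. Wording side by side.** 7.2.3 says patients *will* be withdrawn for substantial non-compliance or protocol violation. 13.1 says deviations *may* lead to withdrawal. 8.5 answers missed diary days with a reminder call and gives 80% to 120% as acceptable drug compliance. No diary threshold is given, and the parenthesis in 7.2.3 can mean diary and drug together or either one.

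**2. Visits no longer scheduled.** Table 1 has post-baseline bile acid visits at Weeks 4, 12, 22, 24, 36, 46, 48, 60, 70 and 72, which is 10. Growth is evaluated at Weeks 24, 48 and 72. Visit 12 is withdrawal week + 4; the gap is 70 − Visit 12 week.

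| Withdrawn at week | Bile acid visits lost | Visit 12 at week | Gap to Week 70 (weeks) | Growth points lost |
|---|---|---|---|---|
| 12 | 8 | 16 | 54 | 3 |
| 24 | 6 | 28 | 42 | 2 |
| 48 | 3 | 52 | 18 | 1 |
| 60 | 2 | 64 | 6 | 1 |

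**3. Window check for Week 60.** Latest Week 60 visit: Day 420 + 7 = 427. Visit 12: 427 + 28 + 7 = Day 462. The Week 70 window opens on Day 490 − 7 = 483. The difference is 483 − 462 = 21 days, so Visit 12 cannot stand in for Week 70.

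**4. What is still collected after drug stop.** The early Visit 11 includes bile acids, chemistry, hematology and vital signs with growth measures. Visit 12 includes these and INR. Calls then cover diversion, transplantation and ongoing TEAEs. Later laboratory work (10.2.2.2, 10.2.2.8) is for safety cases only. The gap for bile acids, growth and efficacy laboratory values begins after Visit 12.

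**5. What could be recovered.** A patient kept in the study and on drug can give on-treatment Week 70/72 values. A patient off drug can give only off-drug values at those weeks.

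**6. Added blood for patients off drug** (Appendix 7 tube volumes). Weeks 24, 48 and 72: bile acids 1.1 + chemistry 1.1 + hematology 1.0 = 3.2 mL each, so 9.6 mL. Week 70: bile acids 1.1 + INR 1.4 = 2.5 mL. The maximum is 9.6 + 2.5 = 12.1 mL. All blood for a patient stopping at Week 12: 9.2 + 7.0 + 8.2 + 5.6 + 4.6 = 34.6 mL, plus 12.1 = 46.7 mL. Cohort 2 adds 5.2 + 2.5, giving 54.4 mL.

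**The case against.** The strongest reply is that the endpoint is change after 72 weeks of treatment. A child who stopped at Week 12 cannot supply it. Samples taken long after the last dose, perhaps after diversion or on commercial odevixibat, measure something else. The study is open label, unrandomised, without formal hypothesis testing and mainly descriptive, so off-drug follow-up has no randomised comparison to protect. This stands, and it limits the second part of the point: off-drug visits do not restore the primary end value.

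A reader might also infer that 11.2.2.2 is contradicted or not carried out at all. The documents do not support that. Visit 11 at withdrawal and Visit 12 at 28 days off drug collect efficacy measures, and the calls cover diversion and transplantation, which are secondary endpoints. The commitment is soft and partly met. Section 11.2.2.5 also tests change from baseline 1 to end of treatment, and missing-data detail is left to a SAP that is not shown.

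On compliance, 8.5 does give a yardstick for drug, and reminder calls can be read as the step before substantial non-compliance. 13.1 and 7.2.3 can be reconciled if minor deviations may, and substantial ones do, lead to withdrawal. Section 10.2.2.7 allows re-challenge, so not every stop is final. All of this stands. None of it changes the effect of the mandatory bullet once it applies: a patient able to give an on-treatment sample is removed.

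**Conclusion.** The point holds as a cheap improvement. A stated rule in 7.2.3 discards on-treatment Week 70/72 bile acid, growth and laboratory values that could be obtained, although the full analysis set keeps every dosed patient. Separately, efficacy collection after drug stop is only partly carried out.

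Per patient, withdrawal at Week 60 or earlier leaves no scheduled sample for either week of the end value. These counts come from the calendar and hold for any early withdrawal, including withdrawal of consent, which no wording repairs. They therefore do not measure the effect of the non-compliance bullet alone.

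It would be tempting to attach a patient count or a direction of bias. The document gives no dropout rate and no number of non-compliant patients. If 10%, 20% or 30% of the approximately 120 patients were withdrawn by Week 60 for any reason (an assumption), 12, 24 or 36 would lack both samples. The share due to this rule is unknown, and the direction of any bias cannot be determined.

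**What to change.** **Main change.** In 7.2.3, replace the non-compliance bullet with a statement that substantial eDiary or study drug non-compliance, or a protocol violation, is followed up and documented under 8.5 and is not by itself a reason for study withdrawal. The investigator and sponsor decide whether drug continues. Keep the best-interest bullet. Align 13.1, so that deviations are documented and do not by themselves lead to withdrawal.

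**Secondary change.** State in 7.2.3 that stopping drug is not study withdrawal. Unless consent is withdrawn, a transplant has occurred or the pregnancy rule in 10.2.9 applies, ask patients off drug to attend those of the Week 24, 48, 70 and 72 visits still ahead. These cover bile acids, growth and laboratory tests, with INR at Week 70 for PELD/MELD. Keep Visits 11 and 12 at drug stop and the calls. List the visits in 7.1.1 and Table 1, footnote b. Flag the values as off drug, note any diversion or commercial odevixibat, and report them separately from the on-treatment change. This carries out 11.2.2.2 and informs growth and liver outcomes.

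**Cost.** Wording in four places. Some patients with thin diary or dosing records stay in the study. Patients off drug have at most four already scheduled visits and about 12.1 mL of blood. A patient stopping at Week 12 would give at most 46.7 mL in all (Cohort 2: 54.4 mL), against 80.5 mL (88.2 mL) planned for the full study.
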